3. Research Proposal

TITLE OF RESEARCH PROPOSAL

Feasibility Randomised Controlled Trial of Intensive Music Therapy on Cognitive Function in Subacute Stroke Rehabilitation in Malaysia

KEY WORDS

Music therapy; randomised controlled trial; rehabilitation; stroke; cognition; attention

BACKGROUND/ JUSTIFICATION

Stroke is a leading cause of long-term disability worldwide, often resulting in cognitive impairments, particularly in memory, attention, and executive function, which significantly impact patients' quality of life and daily functioning. Research indicates that music therapy can enhance cognitive recovery during neurorehabilitation by engaging multiple brain networks and promoting neuroplasticity. There is still limited evidence on the specific effects of intensive music therapy during the subacute phase, a critical period for neurorehabilitation. In addition, there is no published report on the efficacy of structured music therapy as part of a cognitive rehabilitation program in Malaysia, despite a concerted move to promote the use of music for therapeutic purposes in this country over the last decade. Music therapy has not been a part of a formal therapeutic modality in most neurorehabilitation program locally, unlike the more established music therapy practice in neighbouring countries such as Singapore. This study proposes to investigate the effects of intensive music therapy on cognitive functions in subacute stroke patients, while also assessing its feasibility within regular rehabilitation program in Malaysian setting. If successful, this approach could support the integration of music therapy into clinical neurorehabilitation settings, promoting its wider use for cognitive recovery post-stroke.

OBJECTIVES/OUTCOMES

Objectives:

- 1. To assess the feasibility of recruiting, retaining, and ensuring adherence of subacute stroke patients to an intensive music therapy program within a neurorehabilitation setting.
- 2. To evaluate the practicality of integrating music therapy into existing stroke rehabilitation protocols, including the training requirements for staff, resource availability, and logistical considerations.
- 3. To gather preliminary data on the impact of intensive music therapy on cognitive function, specifically memory, attention, and executive function, to estimate effect sizes and inform the design of a larger, fully powered randomized controlled trial.

Expected outcomes:

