A sample of 30 subacute stroke patients (15 control and 15 intervention) will be recruited from the UMMC rehabilitation ward. This number is chosen based on practical considerations to evaluate feasibility metrics and exploratory analysis as in the objectives. For these purposes, a sample size of 30 is typically adequate to gather enough information about the practical aspects of the trial. This number could also ensure that the feasibility objectives are met even with at least 20% dropouts. The average stroke admission to the rehabilitation ward in UMMC is five patients per week, and the number of potential patients that will be eligible is estimated about 2 per week. This total number of 30 will be sufficient within the study period and the grant duration.

Statistical Analysis:

Descriptive Statistics and Exploratory Inferential Statistics will be used in this study.

The means, standard deviations, and 95% confidence intervals (CIs) for cognitive outcome measures (e.g., memory, attention, executive function scores) at baseline, post-intervention, and

follow-up will be used. This will provide a preliminary understanding of the data distribution and effect sizes.

For the exploratory Inferential Statistics, independent t-test (or Mann-Whitney U Test) will be used to compare the mean changes in cognitive scores between the intervention and control groups. The independent t-test if the data are normally distributed. If not, we will use the Mann-Whitney U test as a non-parametric alternative.

Within each group, we will compare the baseline and post-intervention scores using the paired t-test for normally distributed data or the Wilcoxon signed-rank test for non-parametric data. Cohen's d will be used for independent t-tests (between groups) or r for non-parametric tests.

A repeated measures ANOVA (if the data is normally distributed) or a mixed-effects model will be used to explore changes over time (baseline, post-intervention, and follow-up). Given the small sample size, these analyses will likely be underpowered but can provide estimates of variability and preliminary trends.

RESEARCH DATA

Where will the data be kept?

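### At 12 to 15 patients per arm, uncorrected Cohen's d is biased away from zero by about 3%; Hedges' g would remove this small systematic error

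*Protocol*

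**What the plan says.** The Statistical Analysis section plans that an "independent t-test (or Mann-Whitney U Test) will be used to compare the mean changes in cognitive scores between the intervention and control groups". For the size of the effect it then says: "Cohen's d will be used for independent t-tests (between groups) or r for non-parametric tests". It gives no formula and does not mention a small-sample correction.

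The Objectives section, item 3, gives the purpose: preliminary cognitive data are collected "to estimate effect sizes and inform the design of a larger, fully powered randomized controlled trial". The Potential Impact section repeats that preliminary effect sizes should feed larger studies.

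The Sample size calculation section fixes the numbers: "A sample of 30 subacute stroke patients (15 control and 15 intervention) will be recruited from the UMMC rehabilitation ward". It adds: "This number could also ensure that the feasibility objectives are met even with at least 20% dropouts".

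Other summaries are planned as well, namely "The means, standard deviations, and 95% confidence intervals (CIs) for cognitive outcome measures" at each time point. No interval for the effect size itself is mentioned. The inferential analyses are labelled exploratory, and the paragraph on change over time concedes that power will probably be low.

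**The concern.** Cohen's d divides the difference in means by the pooled sample SD. In small samples the reciprocal of that SD is on average too large, so d is on average too far from zero. This is separate from imprecision. The low power that the protocol concedes concerns how widely d scatters, not where it is centred.

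In most trials the point would be cosmetic. Here the effect size is a stated product and is meant to size the next trial. Required sample size varies with one over the square of the effect, so a 3% error in d becomes an error of 5% to 7% in the sample size, in the direction of too few patients.

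**Working it through.** The protocol gives no target effect, power or significance level for its own sample size, so there is no figure of its own to reproduce. The check is on the named index.

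**Inputs from the protocol.** 15 per arm, so df = 15 + 15 − 2 = 28. With 20% dropout, 30 × 0.8 = 24 patients remain; if losses are even, that is 12 per arm and df = 22.

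**Assumptions, not in the protocol.** Normal change scores with equal SDs; d computed with the pooled SD and no correction; a true effect δ of 0.5 SD, with 0.2 and 0.8 as a range; a later 1:1 trial with 80% power at two-sided 5%.

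**Step 1: the bias.** The expected value of d is δ / J, where J = Γ(df/2) / [√(df/2) × Γ((df − 1)/2)].

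| Per arm | df | J | 1/J | Bias | Expected d if δ = 0.5 |
|---|---|---|---|---|---|
| 15 | 28 | 0.973 | 1.028 | 2.8% | 0.514 |
| 12 | 22 | 0.965 | 1.036 | 3.6% | 0.518 |

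A simulation of 200,000 trials at 15 per arm with δ = 0.5 gave a mean d of 0.515, in agreement.

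**Step 2: bias against noise, 15 per arm, δ = 0.5.** The bias is 0.514 − 0.500 = 0.014. The large-sample standard error is √(2/15 + 0.5²/60) = 0.371, and the exact SD of d from the noncentral t distribution is 0.386, hence about 0.38. The bias is therefore about 4% of one standard error. The central 95% of d values runs from −0.22 to 1.30.

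**Step 3: a later trial sized on the expected d.** Per arm, n = 2 × (1.960 + 0.842)² / d² = 15.70 / d².

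- True effect: 15.70 / 0.5² = 62.8, so 63.
- Expected d from 15 per arm: 15.70 / 0.5139² = 59.4, so 60.
- Expected d from 12 per arm: 15.70 / 0.5179² = 58.5, so 59.

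Before rounding, the shortfall is 1 − J², which is 5.3% at 28 df and 6.8% at 22 df. Using the t distribution instead of the normal gives 61 against 64 for the 15-per-arm case, the same gap of three.

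Over the range of effects, for a pilot of 15 per arm:

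| True δ | n per arm on true δ | n per arm on expected d | Actual power |
|---|---|---|---|
| 0.2 | 393 | 372 | 77.9% |
| 0.5 | 63 | 60 | 78.2% |
| 0.8 | 25 | 24 | 79.1% |

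**Step 4: effect of the correction.** Hedges' g = J × d has expected value δ. At δ = 0.5 and 15 per arm, the root mean squared error is 0.386 for d and 0.375 for g. The correction removes the mean bias and also reduces the total error slightly.

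**The case against.** The strongest objection is that the protocol names a measure, not a formula. Correction factors are commonly settled in the SAP, which is not at hand, and nothing in the protocol rules one out. That stands to this extent: the point applies only if d is left uncorrected. But the protocol does name the index, and a reader following it literally would compute plain d.

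Second, the bias is trivial beside the scatter, and the later trial loses only 1 to 2 points of power. This is true, and it limits the point to a minor refinement.

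Third, in terms of the median, g is further from the truth than d (0.491 against 0.505 for a true 0.5), so a single trial is about as likely to overstate as to understate with either index. This is correct, but it does not outweigh the removal of the mean bias together with a lower mean squared error.

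Fourth, nothing is lost for good: anyone with d and the arm sizes can multiply by J afterwards. That is so, although the headline figure is the one most likely to be carried forward.

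A reader might also infer that the r named for non-parametric tests is faulty, because Z/√N cannot exceed 0.852 at 15 against 15 without ties and rises with ties under complete separation. The protocol does not support this. It does not define r, and a rank-biserial r reaches 1. Complete separation of the arms is also unrealistic: in a simulation at 0.5 SD, r was slightly lower, not higher, on an assumed four-level score (0.224 against 0.235 untied). The probability of superiority also moved with ties there (0.638 to 0.626), so it would be no clear improvement.

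**Conclusion.** The point holds as a minor refinement. Uncorrected d overstates the absolute standardised difference on average by 2.8% at 15 per arm and 3.6% at 12 per arm. For a true effect of 0.5 SD, that means about three fewer patients per arm in a later trial when the pilot keeps 15 per arm, and four fewer when it keeps 12. These figures rest on normal change scores with equal SDs, no correction being applied, even dropout, and the assumed design of the later trial.

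Two stronger readings are not supported. The effect sizes are not seriously distorted, since sampling error is some 25 times the bias (0.38 / 0.014 ≈ 27). Nor does d inherently favour the intervention. The bias is multiplicative and points away from zero: it vanishes if there is no true effect and favours control if control is better.

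**What to change.** In the Statistical Analysis section, replace Cohen's d with Hedges' g for the between-group comparison, computed as d times J with df = n1 + n2 − 2 from the patients actually analysed (0.973 at 28 df, 0.965 at 22 df), and report it with its 95% confidence interval. The interval matters more than the correction, because it shows those planning the larger trial how little the point estimate settles.

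The cost is one sentence, with no extra data or patients. The reported effect becomes about 3% smaller in absolute size: 2.7% at 28 df and 3.5% at 22 df. On this point the wording on r does not need to change.

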- 1. The study successfully recruits and retains the target number of subacute stroke patients, with a high adherence rate to the intensive music therapy sessions.
- 2. The intervention is effectively integrated into the existing stroke rehabilitation program, with staff adequately trained and resources efficiently utilized.
- 3. Preliminary data show trends of improvement in cognitive functions (e.g., memory, attention, executive function) among patients receiving music therapy

METHODOLOGY

Study design

This study will be a feasibility randomised controlled trial (RCT) in one centre, with two parallel groups: an intervention group receiving intensive music therapy in addition to standard neurorehabilitation, and a control group receiving only standard neurorehabilitation. A certified music therapist will conduct the intervention and a trained assessor will evaluate the outcome. The assessor is blinded to the patients' allocation group and will evaluate the cognitive outcomes at baseline, at two weeks (after 8 sessions) and at 1 month post intervention. All patients who

are admitted to the rehabilitation ward for stroke rehabilitation will be screened and approached. Informed consent will be obtained from eligible patients before randomisation.

To ensure that there are exactly 15 patients in both the control and intervention groups, block randomization will be used using a random number generator. After randomization, the group assignments will be kept in a password-protected file that only the study coordinator can access. The assessor will not have access to this information because the patients will be labelled with anonymous codes that do not reveal whether they are in the control or intervention group. The assessor will only know the code, not the group assignment, ensuring unbiased evaluation.

Intervention group

The music therapy session described follows a structured and engaging approach, aimed at enhancing the patient's cognitive skills during neurorehabilitation. Here's a summary of the session components:

1. Relaxation Phase: The session begins with a five-minute deep breathing exercise to help the participant relax and prepare mentally for the activity.

2. Song Selection: The therapist presents a list of 50 well-known pop songs from the past three decades, available in four languages (Malay, English, Mandarin, and Tamil). The participant chooses a song based on personal preference, promoting cultural relevance and personal connection.

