 Communication and Language Therapy: Speech-language pathologists work with patients to improve verbal and non-verbal communication, focusing on both comprehension and expression.
 Problem-Solving Exercises: These help patients break down real-life problems into smaller, manageable steps, encouraging better decision-making skills.

The control group's daily rehabilitation sessions will last for 45 minutes, mirroring the music therapy group's session duration, ensuring a fair comparison of outcomes across both groups. This comparison will help assess the unique contributions of music therapy on cognitive functions like attention, memory, and executive functions in stroke patients.

Inclusion Criteria:

- 1. Diagnosed with ischemic or haemorrhagic stroke confirmed by CT scan
- 2. Duration of stroke within the first 3 months
- 3. Aged 18 75 years old
- 4. Ability to provide informed consent
- 5. Understands Bahasa Melayu or English with basic communication abilities to follow instructions during therapy sessions
- 6. Mild to moderate cognitive impairments with MoCA score of 10-25.

Exclusion Criteria:

- 1. Severe aphasia
- 2. Significant uncorrected hearing or visual impairments preventing engagement in music therapy.
- 3. Severe or unstable medical conditions (e.g., uncontrolled hypertension or diabetes).
- 4. Medications that significantly impair cognition or motor function (e.g., high-dose sedatives).
- 5. History of neurological diseases other than stroke (eg, Parkinson's disease).

Outcome measures

This will be assessed at baseline, after completion of 8 sessions and also at 1 month after completion. Primary outcome measures are Montreal Cognitive Assessment (MoCA), Trail Making Test (TMT), Digit Span (Forward and Backward) and Clock Drawing Test (CDT). The secondary outcome measure is MBI.

Sample size calculation:

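### Normality is the only stated criterion for choosing between repeated measures ANOVA and a mixed-effects model in the exploratory three-visit analysis, and it does not separate ANOVA from a standard linear mixed model

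*Protocol*

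**What the plan says.** Under Study design, a blinded assessor "will evaluate the cognitive outcomes at baseline, at two weeks (after 8 sessions) and at 1 month post intervention". Outcome measures names several cognitive tests as primary: MoCA, TMT, Digit Span and CDT.

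Statistical Analysis then sets three rules that depend on normality.

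- **Between arms:** an "independent t-test (or Mann-Whitney U Test) will be used to compare the mean changes in cognitive scores between the intervention and control groups". The t-test applies to normal data, and the fallback is explicit: "If not, we will use the Mann-Whitney U test as a non-parametric alternative".
- **Within arm:** the paired t-test, or Wilcoxon signed-rank where the data are not normal.
- **Across the three visits:** "A repeated measures ANOVA (if the data is normally distributed) or a mixed-effects model will be used to explore changes over time".

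Cohen's d "will be used for independent t-tests (between groups) or r for non-parametric tests". Of the three-visit analysis, the section concedes that "these analyses will likely be underpowered but can provide estimates of variability and preliminary trends". It gives no type of mixed model, link or distribution, and does not mention missed visits or covariance structure as grounds for the choice.

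**The concern.** In the first two rules, the alternative is a rank method that drops the normality assumption. The third rule follows the same pattern, but its alternative does not do this job. A standard linear mixed model assumes normal residuals and normal random effects, so a score that fails the check would move to a model with the same assumption.

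The differences that should drive the choice are not mentioned. Repeated measures ANOVA, as conventionally run, discards any patient without all three visits, whereas a mixed model keeps every observed visit. ANOVA also fixes the covariance structure, which a mixed model can estimate.

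If the rule is applied score by score, a normality check could put one primary score on completers only and another on everyone observed. Objective 3 uses these preliminary data to inform a larger trial, so the estimates of variability should rest on a common set of patients where possible.

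**Working it through.** The protocol states no figure for this analysis, so there is none to reproduce. Two questions can be checked.

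**1. Does normality separate the methods?** Data were simulated for 15 patients per arm at three visits, with assumed means and variances. The arm-by-visit F from repeated measures ANOVA was compared with that from a random-intercept linear mixed model fitted by REML.

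| Data | Patients (rows) in ANOVA | F, ANOVA | Patients (rows) in mixed model | F, mixed model |
|---|---|---|---|---|
| Normal, complete | 30 (90) | 0.7350 | 30 (90) | 0.7350 |
| Skewed, complete | 30 (90) | 2.4881 | 30 (90) | 2.4881 |
| Normal, 6 of 30 miss visit 3 | 24 (72) | 1.3078 | 30 (84) | 1.0014 |
| Skewed, 6 of 30 miss visit 3 | 24 (72) | 2.5016 | 30 (84) | 2.1636 |

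The F values depend on the simulated inputs, but the pattern does not. With balanced data, compound symmetry and a positive between-patient variance estimate, the two tests coincide whether or not the data are normal. They part when visits are missed.

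**2. How much precision is at stake?**

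Inputs from the protocol: 15 per arm and three visits. Assumed: random loss of 3 per arm (30 x 0.8 = 24 complete), unit SD, and an equal between-visit correlation r of 0.3 to 0.8. The 20% loss is borrowed from Sample size calculation; the correlation is not in the document.

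For a between-arm difference in change with n patients per arm, SE = sqrt(4(1 - r)/n). At r = 0.5, 12 completers give sqrt(2/12) = 0.408 and 15 give sqrt(2/15) = 0.365.

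The ratio of the complete-case SE to the mixed-model SE depends on when patients leave:

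- *All lost after two weeks, two-week contrast:* sqrt(15/12) = 1.118, for any r.
- *All lost after two weeks, 1-month contrast:* sqrt[2(1 + r)/(1.8 + 2r)]. At r = 0.3 this is sqrt(2.6/2.4) = 1.041; at r = 0.8 it is sqrt(3.6/3.4) = 1.029.
- *All lost before two weeks, either contrast:* sqrt[2/(1.8 + 0.2r)]. At r = 0.3 this is sqrt(2/1.86) = 1.037; at r = 0.8 it is sqrt(2/1.96) = 1.010.
- *Half lost before two weeks:* 1.066-1.080 at two weeks and 1.020-1.039 at 1 month.

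The complete-case SE is therefore 1-12% larger at two weeks and 1-4% larger at 1 month.

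The between-arm effect size is tied to the planned t-test on change, which uses every patient with both visits of the pair. Its SE relative to the mixed model is:

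| Timing of loss | Two weeks | 1 month |
|---|---|---|
| All after two weeks | 1.000 | 1.029-1.041 |
| Half before two weeks | 1.005-1.018 | 1.020-1.039 |
| All before two weeks | 1.010-1.037 | 1.010-1.037 |

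The net loss is 0-4%. At 10% loss it is 0-2%, and the complete-case excess at two weeks is 0.5-5%.

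A simulation with an unstructured covariance estimated from the data (40,000 replicates per case) agrees. The t-test to mixed-model ratio was 1.000-1.034 at two weeks and 1.006-1.035 at 1 month. The complete-case ratio at two weeks was 1.005-1.119.

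**The case against.** **The routing is partly inferred.** A reader might infer that the protocol requires normal scores to be analysed by ANOVA. It does not say so. The condition restricts the ANOVA to normal data, while the mixed model is offered without a condition and without the explicit fallback wording used for Mann-Whitney. A mixed model for every score would already comply. This stands, so loss of incomplete patients is something the text permits and suggests, not something it imposes. Normality is still the only criterion offered on either reading.

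**The mixed model need not be linear.** In a generalised mixed model the distribution would be a relevant criterion. That is fair, but none is named, and the point is limited to the standard linear form.

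**Sphericity.** A reader might infer that the planned ANOVA would have inflated error rates because normality does not secure sphericity. The protocol is silent on this and does not rule out a Greenhouse-Geisser correction, which is routine. No error-rate claim is made here.

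**The 20% is not a forecast.** Sample size calculation says "This number could also ensure that the feasibility objectives are met even with at least 20% dropouts". That is a tolerance for the feasibility objectives, so the loss used above is an assumption.

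**The stakes are low.** The 12% arises only at two weeks when all loss comes later, which is exactly where the planned t-test loses nothing. Means, SDs and confidence intervals at each visit are planned as well, so variability estimates do not depend on this analysis alone. This stands and sets the severity.

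**Conclusion.** The concern holds as a minor point about a badly chosen criterion. The protocol states a selection rule, so this is more than detail left to an analysis plan, and a plan that followed the rule would inherit it. Normality does not distinguish repeated measures ANOVA from a standard linear mixed model; missed visits and covariance structure do.

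The 12% upper figure should not be read as damage to the effect size carried into a larger trial. It belongs to the longitudinal analysis alone, and the net loss of 0-4% is the relevant size. These figures assume random loss and equal between-visit correlations. No bias is claimed, no feasibility outcome changes, and the analysis is exploratory by the protocol's own account. The change is optional but worthwhile (severity: COULD).

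**What to change.** Drop the normality condition and replace the sentence with text such as:

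*For each cognitive score, change across the three visits will be explored with one mixed-effects model fitted to all observed visits, with arm, visit and arm-by-visit as fixed effects, an unstructured within-patient covariance and small-sample degrees of freedom. If the model does not converge, a simpler covariance structure will be used and reported. Residuals will be checked. If they are clearly non-normal for any score, a suitable transformation (for example, log TMT time) or a bootstrap interval will be given as a sensitivity analysis.*

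The residual step covers every score, so that MoCA, Digit Span and CDT also have a remedy. The planned t-test or Mann-Whitney comparisons and the paired tests stay as they are.

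The cost is one sentence and slightly more software set-up, with no extra data or visits. The gain is small if few visits are missed. A compound-symmetry fallback would bring back the ANOVA's covariance assumption, which is why its use should be reported.
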